## Section 1.2 Research Questions

The purpose of the proposed project is to contribute to and improve upon the existing weight management and physical-activity-promoting programs available to veterans. Our specific objectives are to:

- 1) Assess the effectiveness of VA MapTrek as a whole to increase steps per day in veterans compared to the control group.
- 2) Assess the effectiveness of challenges within VA MapTrek to increase steps per day in veterans in the intervention group.
- 3) Identify additional areas of development within the MapTrek program to improve its future efficacy among veterans.

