### Section 2.4 Approaching the Patient

If you believe a patient is eligible for the study based on their CPRS data and discussions with the medical staff, approach the patient to see if they are interested in learning more and to finish any screening questions. You should only approach patients upon approval from the medical staff so that you don't disrupt clinic flow. Here is an example script (feel free to say in your own words as long as the major points are covered):

*"We are conducting a study with eligible participants to see if our map-based race will encourage Veterans to take more steps per day. We will randomize the participants to 2 different groups, a control group and an intervention group. The control group will receive a Fitbit, which is a small device that is worn on your wrist that measures your movements, to wear for approximately 9 weeks. At the end of the 9 weeks, they will complete an exit survey via phone call or online.*

*The intervention group will also be given a Fitbit and asked to wear it for approximately 9 weeks, but they will also be enrolled in a map-based race. You will be notified about your progress in the race via text message and you may also receive challenges where you can earn extra steps in the race. At the end of the 9 weeks, they will also complete an exit survey that asks about their experiences with the study.*

*Is this something that you'd like to learn more about or might be interested in participating in?"*

If the person indicates that they'd like to learn more about the study or want to participate, be sure to complete any remaining fields on the Screening Survey (Appendix A).

If any of these criteria are not met, the person is ineligible for the study. Please explain the reason for their ineligibility and thank them for their time.

If all criteria are met, you should continue on with the informed consent procedures in a room that is approved by the medical staff to avoid disrupting the clinic flow.

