VA MapTrek- Yr 2

IRB #: 201901762

Statistical Analysis Plan

Creation Date: 6/7/2024

VA MapTrek **Statistical Analysis Plan**

We only used data from after the start of the intervention in our analysis; the baseline data was not used to estimate the model. We defined the start date of the intervention as Day 0 for all participants.

Statistical analysis was done using Bayesian mixed effects linear regression. We included fixed effects for day-of-week, days since the start of the intervention period, group indicator (Intervention Group versus Control Group), and an interaction between group and days since intervention period start. We included two random effects: random intercept and random slope by participant. The random effects were modeled using a bivariate normal distribution.

We included vague priors on all parameters. All model fixed effects had priors of $U(-\infty, +\infty)$. We imposed slightly limited priors on the standard deviation of step counts within a person and the on-diagonal values of the covariance matrix for the random effects of $U(0, 25,000)$. This upper bound of 25,000 was at 4-5x greater than the largest plausible values for these values and was set to accelerate sampling. The off-diagonal elements of the covariance matrix were given a Lewandowski, Kurowicka, and Joe prior with a shape parameter of 2. Our prior belief is that the random slope and intercept values will be correlated but we are very uncertain about the extent of that correlation. A shape parameter of two provides a weak prior in favor of correlation.

We estimated the model using Bayesian Hamiltonian Monte Carlo (HMC) simulation using Stan No-U-Turns sampler (NUTs). We ran 6 chains for 25,000 draws on each chain. We discarded the first 5,000 draws as burn-in and assumed the remaining 20,000 draws per chain reflected the posterior equilibrium. More convergence was assessed using \check{R} , effective sample size, and the Monte Carlo error relative to the total parameter error.

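### Does the SAP need to name which group contrast from the mixed model answers Objective 1?

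*SAP*

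**What the plan says.** The Protocol's Section 1.2 gives Objective 1 as "Assess the effectiveness of VA MapTrek as a whole to increase steps per day in veterans compared to the control group". The example script in Section 2.4 puts the purpose the same way: "to see if our map-based race will encourage Veterans to take more steps per day". Neither gives a time point or an averaging window.

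The SAP is one page. On data it says "We only used data from after the start of the intervention in our analysis", and on the time origin "We defined the start date of the intervention as Day 0 for all participants". On the model it says "Statistical analysis was done using Bayesian mixed effects linear regression". The fixed effects are day of week, days since start, a group indicator and "an interaction between group and days since intervention period start", with a random intercept and slope per participant. Fixed effects have flat priors. The sampler paragraph says the authors "assumed the remaining 20,000 draws per chain reflected the posterior equilibrium", and the text ends with convergence diagnostics. It names no contrast, last day, interval level, posterior probability or threshold. The page carries "Creation Date: 6/7/2024" and is in the past tense throughout.

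**The concern.** With an interaction in the model, no single coefficient is the treatment effect. Under 0/1 group coding and uncentred days, the group coefficient is the difference on Day 0, before the races have had time to act, and the interaction is the difference in daily trend. Neither is the average difference over the race period, nor the difference at its end. A reader could meet any of these reported as the answer to Objective 1.

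Timing sharpens the point. The SAP reads as a report of a finished fit, so nothing in the documents shows that a contrast was fixed before the posterior was seen. If the most favourable of several intervals could be presented, the chance of a positive reading when the programme does nothing would exceed the 5% that goes with one named contrast.

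**Working it through.** The documents give no sample size, effect size, variance estimate or decision rule, so there is no design figure to reproduce. The check has three parts.

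**1. What the model yields.** Write b_G for the group coefficient and b_GD for the interaction. The group difference on day t is D(t) = b_G + b_GD × t. Section 1.3 of the Protocol gives eight week-long races. The SAP does not state its window, so assume 8 × 7 = 56 days numbered 0 to 55, with mean day 27.5.

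| Reading | Formula | Unit |
|---|---|---|
| Day-0 difference | b_G | steps/day |
| Difference in trend | b_GD | steps/day per day |
| Period average | b_G + 27.5 × b_GD | steps/day |
| Day-55 difference | b_G + 55 × b_GD | steps/day |

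All four come from the same joint posterior. If b_GD is zero, the three steps-per-day readings coincide. If not, they part. As an illustration only, b_G = 500 and b_GD = −10 give +500 on Day 0, 500 − 275 = +225 on average and 500 − 550 = −50 on Day 55.

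The exact window matters little for the average. Counting only the 48 Monday-to-Saturday race days, with Day 0 a Monday, moves the mean day from 27.5 to 27.0. In this illustration the average then moves from +225 to +230.

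**2. How large the multiplicity could be.** Assume no true effect, and a reading rule that counts any 95% interval excluding zero; this rule is not in the SAP. With flat fixed-effect priors, the large-sample normal approximation applies. The covariance of a participant's intercept and slope is Ψ + σ²(Z′Z)⁻¹, where Ψ is the random-effects covariance, σ the within-person SD and Z = [1, t] for t = 0 to 55. With equal arms and complete data, arm size cancels.

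Assumed values, in all combinations (3 × 3 × 4 × 3 = 108 sets):
- intercept SD 2,000, 3,000 or 4,000;
- slope SD 15, 30 or 45 steps/day per day;
- intercept–slope correlation −0.5, −0.25, 0 or 0.25;
- within-person SD 2,000, 3,000 or 4,000.

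Share of simulated draws with at least one |z| above 1.96:

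| Readings allowed | Range | Median |
|---|---|---|
| One named contrast | 5.0% | 5.0% |
| Average, Day 55 | about 5.6–7.8% | about 6.4% |
| Day 0, average, Day 55 | about 6.3–11% | 8.1% |
| Both coefficients | 8.8–9.8% | 9.6% |
| Both coefficients and the average | 10.0–11.9% | 10.9% |
| All four | 10.7–13.2% | 11.8% |

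Whatever the variances, and for any number of combinations of the two coefficients, the ceiling is P(χ² on 2 df > 1.96²) = exp(−1.96²/2) = 14.65%.

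The SAP's remark that 25,000 is four to five times the largest plausible SD implies 25,000/5 = 5,000 to 25,000/4 = 6,250, above this grid. Widening it (SDs to 6,250, slope SD 5 to 60, correlation −0.7 to 0.5) gives 9.7% to 13.1% for all four readings, so the conclusion is stable.

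**3. What a change would buy.** Reporting all four with 95% intervals, equal prominence and no primary contrast leaves the four-reading figure at 10.7–13.2% for anyone who reads them by the same rule. Naming one contrast now would give 5% only if the choice had been made before the fit, and an addition written after the fit cannot establish that.

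**The case for a change.** The best case for a change is that the silence concerns the main objective, that the document was written after the fit, and that a remedy costs one paragraph and two derived quantities per draw. Even an analyst who reports only the two coefficients leaves two chances, at 8.8% to 9.8%, and still gives no average in steps per day. Nor does the wording of Objective 1 settle the matter: its reference to the programme in its entirety contrasts with the challenges in Objective 2, so it concerns components, not time.

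Much of this stands. The documents do leave the contrast, window and posterior summary open, and the arithmetic is right under its assumptions. Three things weaken the inference to a needed change:

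- The exclude-zero rule is supplied from outside. The SAP describes estimation and claims no test.
- The trend coefficient is not in steps per day, the unit of Objective 1. Without it the median falls from 11.8% to 8.1%, so calling the risk about twice 5% depends on counting the trend as an answer.
- Past tense and a 2024 date show when this page was written. They do not show that results drove a choice, or that no earlier plan existed.

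**Conclusion.** The omission is real but does not require a change to the plan. The model suits repeated daily counts, and a competent analyst can obtain every sensible contrast from the one fit. The period average, in the unit of Objective 1, is an obvious summary to set beside the two coefficients. Whether to name one primary contrast or to show several is a choice on which reasonable statisticians differ, and neither course recovers pre-specification once the fit is done.

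Under an assumed exclude-zero rule, the exposure is about 6% to 11% for the three steps-per-day contrasts and about 11% to 13% for all four, against 5% for one fixed in advance. These ranges assume a 56-day window, complete data, equal arms and the variance grid above. Only the 14.65% ceiling is free of the variances, and it too uses the normal approximation. A reader of the results should check which contrast and which days a reported figure refers to.

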## Section 1.3 Project Outline

All consented participants will be provided with a Fitbit and instructed to wear it all day, every day for the next 9 weeks (The first few participants may require an additional week or two of wear as we will not begin the first MapTrek race until we have at least 5 participants enrolled in the study. They will be told this upon enrollment.). We expect the enrollment process to take anywhere from 15 to 45 minutes, depending on group assignment and participant familiarity with using Fitbits.

This, plus an exit survey (given via text message or phone, whichever the participant prefers), will be the extent of participation for the control group.

Members of the intervention group will be instructed on how to use MapTrek, our virtual walking race, and will also be given an instruction packet to refer to later. Data collected during the first week from the Fitbit will be used to compute baseline activity level. This baseline data will be used to place participants into an appropriate initial race group. Participants are placed into groups with other individuals who are active at a similar level, so that groups will be competitive.

Each virtual walking race will begin on Monday morning and end on Saturday night. Results of each race will be announced on Sundays. Depending on their performance each week, group assignment may change. Participants will compete in 8 week-long races over the course of the study.

Participants will receive 2-4 text messages per day including a daily status report and a link to view the race. They will also periodically receive challenge messages. If a participant completes a challenge, they will be awarded bonus steps to help move them along the route quicker.

To win a race, a participant must be furthest along on the route at 11:59 pm on Saturday. There is a leaderboard within MapTrek that helps participants determine their standing within each race. Participants are allowed to choose the screen name displayed on the leaderboard so that they may remain anonymous if desired.

At baseline, we will collect the following data about all participants: first and last name, last 4 of social security number (for consent documentation and to look up records in CPRS), age, sex, race,

ethnicity, marital status, height, weight, body mass index, blood pressure, zip code, current medications, and comorbidities.

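### The SAP model treats intervention participants as independent although they compete in shared race groups; if steps are positively correlated within a race, the interval for group × days would be too narrow

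*SAP*

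**What the plan says.** Protocol Section 1.3 (Project Outline) describes how the intervention is delivered. On the initial race groups: "Participants are placed into groups with other individuals who are active at a similar level, so that groups will be competitive". On later weeks: "Depending on their performance each week, group assignment may change". On duration: "Participants will compete in 8 week-long races over the course of the study". On what members see of each other: "There is a leaderboard within MapTrek that helps participants determine their standing within each race". The same section limits the control arm to a Fitbit and an exit survey. Section 2.6 allocates participants one at a time.

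The SAP's second paragraph specifies a Bayesian linear mixed model. Its fixed effects are day of week, days since intervention start, study arm, and "an interaction between group and days since intervention period start". On the random part it says "We included two random effects: random intercept and random slope by participant" and "The random effects were modeled using a bivariate normal distribution". Neither document describes a race-group term, a multiple-membership term, a robust variance, or a sensitivity analysis for shared races.

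**The concern.** The design is partially nested: allocation is individual, but one arm is treated in interacting groups and the other is not. Seeing and chasing rivals is part of the intervention, so one keen or idle member could shift what the rest of a race group walks that week. A participant intercept and slope absorb correlation within a person. They do not absorb correlation between people in the same race.

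Matching on activity is not the problem, because a stable personal level is carried by the participant intercept. The possible problem is a shared influence that arises within a race. If it exists and is positive, the model counts it as independent evidence from each member. The intervals for the two arm terms, which answer Objective 1 (Protocol Section 1.2), would then understate the uncertainty.

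**Working it through.** The plan has no figure to reproduce: the documents state no sample size, SD, intraclass correlation, race-group size, credible level or decision rule. What follows is a sensitivity calculation. A 95% interval excluding zero is taken as the decision rule, and with the SAP's vague priors the posterior interval is taken to behave like the frequentist one.

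**Inputs**
- From the protocol: 8 weekly races, taken as 56 days.
- Assumed: 50 per arm (n); groups of m = 5 or 10, re-sorted at random each week; daily residual SD 3,000 steps; participant slope SD 25 steps/day per day; shared group-week SD τ of 300 or 600 steps, drawn afresh for each group and week; no true effect; everyone starts together.

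**Step 1: reduce the model.** With balanced data, the planned model compares participants' own fitted slopes between arms.
- Sum of squares of days: 56 × (56² − 1)/12 = 14,630.
- Slope variance without a shared effect: B = 25² + 3,000²/14,630 = 625 + 615.2 = 1,240.2.
- Week midpoints lie ±3.5, ±10.5, ±17.5 and ±24.5 days from the centre, and their squares sum to 2,058. The shared effect therefore adds g = τ² × 49 × 2,058/14,630² = τ² × 0.000471, which is 42.4 at τ = 300 and 169.6 at τ = 600.

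**Step 2: compare true and reported variance of the arm difference in slope.**
- n × true variance = 2B + m·g
- n × variance the model reports = 2B + g − g(m − 1)/(n − 1)
- SE ratio r = √(true/reported); error = 2 × [1 − Φ(1.96/r)]

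| τ | m | n × true | n × reported | r | error |
|---|---|---|---|---|---|
| 300 | 5 | 2,692 | 2,519 | 1.03 | 5.8% |
| 300 | 10 | 2,904 | 2,515 | 1.07 | 6.8% |
| 600 | 5 | 3,328 | 2,636 | 1.12 | 8.1% |
| 600 | 10 | 4,176 | 2,619 | 1.26 | 12.1% |

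Simulation under the same kind of assumptions (40–80 per arm, groups re-sorted on last week's steps, 1,500 replicates) gave 5.7–6.5% at SD 300 and 8.0–11.8% at SD 600. With no shared effect it gave 4–6%.

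**Step 3: average level.** For the period mean, g = τ²/8 = 45,000 at τ = 600. With between-person SD 2,500, B = 2,500² + 25² × 27.5² + 3,000²/56 ≈ 6,883,000. For m = 10, r = √(14,217,000/13,803,000) = 1.015, an error of 5.3%. Week-specific effects hardly reach the average. If group effects persist instead (n = 50, m = 10, between-person SD 3,000, slope SD 30), the period-mean ratio is 1.06 for a group SD of 500 steps with group slope SD 5, and 1.22 for 1,000 with 10.

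**Step 4: sign of the correlation.** For a general within-group correlation ρ of the participant coefficient (n = 50, m = 10), r is 0.88 at ρ = −0.05, 1.00 at 0 and 1.11 at +0.05. Simulated zero-sum rivalry (SD 1,000, m = 10) gave 0.92 for the slope, so intervals would be slightly too wide.

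**Step 5: staggered entry.** The SAP's clock is days since each participant's own start, so one race week can fall at different study weeks for different members. With weekly slope weights proportional to −7, −5, −3, −1, 1, 3, 5, 7, the covariance between two members' slopes, relative to a common start, is 1.00, 0.63, 0.27, −0.03, −0.26, −0.40, −0.42 and −0.29 for entry gaps of 0 to 7 weeks. Much of it cancels. Simulated error for group × days at SD 600:

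| Entry spread over | Error |
|---|---|
| common start | 8–13% |
| 4 weeks | 7.2–10.9% |
| 12 weeks | 6.0–7.8% |
| 26 weeks | 5.1–6.5% |
| 52 weeks | 4.4–5.5% |

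**Step 6: does a race-group × race-week term repair it?** REML fits used 25 per arm, groups of about 8, shared SD 600 and 800 null trials per setting (Monte Carlo SE about 0.8–1.1 points):

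| Entry | Planned structure | With the term |
|---|---|---|
| common start | 10.2% | 5.0% |
| about 8 weeks | 8.1% | 4.5% |
| about 20 weeks | 6.0% | 6.4% |

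With no shared effect, the term widened the interval by under 2%.

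**The case against.** A reader might infer that the planned intervals are too narrow as a matter of fact. The documents do not support that. It requires positive within-race correlation beyond the participant effects, and nothing in either document fixes its sign or size. Each race has one winner, so negative correlation is also conceivable. This objection stands, and the point is conditional.

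A reader might also infer that every group is re-formed each week. Section 1.3 says only that assignment may change.

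The strongest objection to the size is entry. Participants are recruited singly at clinic visits (Sections 2.4–2.6), the first race waits only for five enrolled participants (Section 1.3), and end dates follow each participant's own nine weeks (Section 2.7). Staggered entry is therefore likely, and Step 5 shows that it removes most of the inflation. At SD 300 the excess is small even with a common start. This stands too: the upper figures apply only to compressed enrolment with a large shared effect.

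Finally, Objective 1 asks about MapTrek as a whole, and Step 3 shows that the average level is barely affected by week-specific effects. That is correct. But the model has no single average-effect term. With the interaction present, the arm coefficient is the difference at Day 0 and group × days describes how it changes, so the exposed term is part of the answer to Objective 1.

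None of these objections removes the omission. The model assumes independence where the protocol builds in interaction, and the plan offers no way to check it.

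**Conclusion.** The concern holds in conditional form. Race groups exist in one arm only, and the SAP model assumes independence between people who race together. If steps are positively correlated within a race group in a race week, the interval for group × days would be too narrow. The error of a nominal 5% test would be about 6–12% with a common start, falling toward 5–6% as entry spreads over about 20–26 weeks. The average level is little affected unless group effects persist across weeks.

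All of this rests on assumed inputs: shared SD 300–600 steps, groups of 5–10, and the SDs in the working. The change should be made because the assumption is unchecked and cheap to check, not because the planned intervals have been shown to be wrong.

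**What to change.** Add to the SAP model a random effect for race group × race week, in the intervention arm only and set to zero for controls, with a weakly informative prior on its SD. State how Sunday steps are handled, since races run Monday to Saturday. Take each participant's weekly race-group ID from MapTrek, which needs it to run the races; whether past IDs were kept is not stated. Report the arm and group × days estimates from this model beside those from the planned model, with race-group sizes and the estimated race-group SD. The SAP is written in the past tense, so this can be run on the existing data.

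The cost is one data column, one variance parameter and a somewhat wider interval for group × days. The term has limits. It is poorly estimated if few groups run at once, it cannot represent negative correlation, and it does not capture group effects that fully persist across weeks. The report should say so.

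### The SAP states the random-effects bound on the variance scale, where it would cap the between-person intercept SD at 158 steps/day (probably a wording error), and it reverses the direction of the LKJ(2) prior

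*SAP*

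**What the plan says.** The model in the SAP's second paragraph has a participant-level intercept and slope: "We included two random effects: random intercept and random slope by participant". They are jointly normal, so their covariance matrix is 2×2 with one correlation.

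The third paragraph sets the priors. It opens with "We included vague priors on all parameters". It continues: "We imposed slightly limited priors on the standard deviation of step counts within a person", and extends the same bound to "the on-diagonal values of the covariance matrix for the random effects of $U(0, 25,000"). The reason given is: "This upper bound of 25,000 was at 4-5x greater than the largest plausible values for these values".

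On the correlation it says "The off-diagonal elements of the covariance matrix were given a Lewandowski, Kurowicka, and Joe prior with a shape parameter of 2", and then "A shape parameter of two provides a weak prior in favor of correlation".

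Neither document gives a numerical SD for daily steps, for participants' levels or for their slopes, and neither shows the Stan code.

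**The concern.** Two statements do not agree with what the named quantities are.

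First, one bound and one justification cover three quantities in different units: a residual SD, an intercept variance and a slope variance. A ceiling of 25,000 is generous for an SD in steps/day and very tight for an intercept variance. If the code followed the text, the model could not represent ordinary differences between people in daily steps. That variation would be pushed into the slope and the residual, and the intervals for the group contrasts would be wrong. This would touch the Protocol's first objective (Section 1.2): "Assess the effectiveness of VA MapTrek as a whole to increase steps per day in veterans compared to the control group".

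Second, the LKJ prior is assigned to covariances although it is defined on a correlation matrix. It is also said to lean towards correlation when, at shape 2, it leans towards zero.

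**Working it through.** **1. The bound on each scale (arithmetic on SAP figures only)**

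- Intercept, variance reading: largest SD = √25,000 = 158 steps/day. A bound four to five times the largest plausible variance gives √(25,000/5) = 71 to √(25,000/4) = 79 steps/day as the largest plausible between-person SD.
- Intercept, SD reading: 25,000/5 = 5,000 to 25,000/4 = 6,250 steps/day. Only this reading fits a vague prior.
- Slope, variance reading: slope SD up to 158 steps/day per day, or 158.1 × 55 = 8,696 steps/day over Days 0–55. This does not bind.
- For scale, assumed intercept SDs of 1,000, 2,000 and 3,000 have variances of 1,000,000, 4,000,000 and 9,000,000, which are 40, 160 and 360 times the bound.

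**2. What the cap would do if it was coded**

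Assumed inputs: between-person SD 2,000 or 3,500; within-person SD 3,000 or 3,500; slope SD 25; correlation 0; 25 or 100 participants per arm; complete daily data for 56 days (t = 0 to 55, from the eight weekly races in Protocol Section 1.3).

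Method: with V_true the covariance of one participant's 56 values and V_m the model's version, find the best-fitting bounded model by minimising

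n/2 × [log|V_m| + tr(V_m⁻¹ V_true)] − log(1 − ρ²)

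over intercept SD, slope SD, ρ and residual SD, where n is the total number of participants. Then compare the model SE with the true (sandwich) SE for the group difference at Day 0, at the midpoint t = 27.5 (the average over the study) and in slope. Coverage = 2Φ(1.96 × ratio) − 1.

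| What is bounded at 25,000 | Day 0 SE ratio | Average SE ratio | Group × time SE ratio |
|---|---|---|---|
| Both SDs | 1.00 | 1.00 | 1.00 |
| Slope variance only | 1.00 | 1.00 | 1.00 |
| Intercept variance only | 0.26–0.44 | 0.58–0.72 | 1.48–2.13 |
| Both variances | 0.26–0.44 | 0.58–0.72 | 1.48–2.13 |

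Coverage with the variances bounded:

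- Day 0: 2Φ(1.96 × 0.257) − 1 = 39% to 2Φ(1.96 × 0.440) − 1 = 61%.
- Average: 2Φ(1.96 × 0.584) − 1 = 75% to 2Φ(1.96 × 0.720) − 1 = 84%.

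In every case the fitted intercept SD sits at 158 and the fitted slope SD rises from the true 25 to 46–74. The slope's own ceiling never binds, but the slope is still distorted, because it absorbs variation that the intercept is not allowed to carry.

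**3. Sensitivity to the assumed values**

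- Slope SD 10–50 with correlation −0.3 to 0.3: coverage 74–88% (average) and 39–61% (Day 0); group × time SE 1.0–2.8 times its true size.
- Between-person SD 1,500–4,500, within-person 2,500–4,500, slope SD 10–50, correlation 0: coverage 68–91% and 30–79%; group × time SE 1.1–3.5 times.

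**4. LKJ with shape 2**

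For a 2×2 matrix the density of ρ is 0.75(1 − ρ²), which is highest at ρ = 0.

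- P(|ρ| < 0.5) = 1.5 × (0.5 − 0.125/3) = 0.6875, against 0.50 under a flat prior.
- P(|ρ| > 0.8) = 1 − 1.5 × (0.8 − 0.512/3) = 0.056, against 0.20 under a flat prior.

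The effect on the contrast SEs is about 1%.

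**The case against.** The strongest reply is that this is loose wording and nothing more. The SAP speaks of a covariance matrix even where it assigns an LKJ prior, which belongs to a correlation matrix. That suggests the model was coded as scales plus a correlation, so the diagonal means the SDs. The bound is shared with a quantity expressly called a standard deviation, and the SD reading gives a sensible 5,000–6,250 steps/day. This largely stands, and it makes the harmless reading the probable one. It does not make the text correct, and it cannot replace a look at the code.

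Four stronger readings are tempting and are not supported:

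- *The reported intervals are too narrow.* The documents do not show which scale was coded, and the internal evidence points to SDs.
- *The justification fails on every scale, because an SD bound would imply a largest plausible slope SD of 5,000–6,250 steps/day per day.* This takes the multiple as exact. The sentence is garbled just before it. If *at least* was meant, which is an inference, the SD reading is true of the residual, the intercept and the slope alike.
- *The slope escapes the problem.* Only its ceiling does; if the intercept is capped, the slope and interaction estimates are distorted too.
- *The interaction interval would always be too wide.* With slope SD 50, correlation −0.3, between-person SD 2,000, within-person SD 3,500 and 200 participants in total, the SE ratio is 1.04.

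It is also fair to say that the SAP names no primary contrast. Treating the average difference as closest to the first objective is a judgement.

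**Conclusion.** Both statements are wrong as written; that much rests on the SAP text and simple arithmetic. Damage to the results is possible but not shown. On the probable reading (SDs bounded), the SE ratios are 0.99–1.01 and the correction is purely textual. On the literal reading, the Day 0 and average group differences would be reported with too much confidence, to the extent shown above, while the interaction SE would be inflated or close to right depending on the slope SD and correlation. Every figure on that branch depends on SDs, arm sizes, a correlation and complete data that I have assumed. The LKJ statement is a reporting error, and it leaves the prior at odds with the belief offered in its support.

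**What to change.** 1. Check the Stan code for the scale on which the 25,000 bound was placed, and report it.
2. If it was on SDs, restate the prior as uniform on 0 to 25,000 for the residual, random-intercept and random-slope SDs. Reword the justification as *at least* four to five times the largest plausible value, or say that the bound is far looser for the slope.
3. If it was on variances, refit with the bound on the SDs and correct the text in the same way.
4. In either case, describe LKJ(2) as a prior on the intercept–slope correlation that weakly favours zero.

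The cost is a look at the code and a few corrected sentences, plus one refit only if variances were bounded. No new data or participants are needed.
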